APPENDIX I: What to bring to site

Screening

- Charged iPads
- Charged iPencils
- Compensation in 1 dollar bills, as participants will be paid \$3 per screening
- o Light snacks
- PPE for COVID-19, including face masks, face shields, tissues, Clorox wipes, hand sanitizer, and gloves.

Baseline, immediate follow-up, and 6-month follow-up

- Charged iPads
- Charged iPencils
- Compensation in \$10- and \$5-dollar bills, as participants will be paid \$15 each (Note: for 6-month follow-up please bring \$10 dollar bills as participants will be paid \$30.)
- o Light snacks
- Bottles of water
- PPE for COVID-19, including face masks, face shields, tissues, Clorox wipes, hand sanitizer, and gloves.
- Color coded and labeled vials for saliva collection
- White boxes to store saliva samples
- \circ Cooler with ice
- Drug test kits
- Paper and pens for stress task (trauma imagery task)

Weekly – Health Promotion class

- Charged iPads
- Charged iPencils
- Compensation in \$5 or \$10 dollar bills, as participants will be paid \$10 each
- o Light snacks
- PPE for COVID-19, including face masks, face shields, tissues, Clorox wipes, hand sanitizer, and gloves.
- Teacher manual
- Extra participant book
- o Materials for each week please see teacher manual for weekly supply list

Weekly – MBSR class

- Charged iPads
- Charged iPencils
- Compensation in \$5 or 10 bills, as participants will be paid \$10 each
- Light snacks
- PPE for COVID-19, including face masks, face shields, tissues, Clorox wipes, hand sanitizer, and gloves.
- Extra participant book
- Extra MP3 players
- o Extra yoga mat or two

APPENDIX II: Trauma Imagery Script (Brief Stress Task)

TRAUMA IMAGERY SCRIPT

NOTE TO RA: Make sure the participant has not had anything to eat or drink for one hour and that they had some water to drink at least 10 minutes before starting the task.

RA: Thank you for your participation in this part of the project. We are going to be asking you to recall and describe a stressful or traumatic event. We want to remind you that you can stop at any time if you are uncomfortable, although your participation will help us understand more about the stress process in women who have experienced adversity. The general overview of this procedure is that we are going to take a saliva sample to assess your stress hormones; have you participate in a short stress task; and then take another saliva sample to assess your stress hormones after the task. If this gets to be too intense for you, you can stop at any time. If you experience any severe distress, let me know and we will stop the task and immediately contact your onsite clinician/therapist. I want to remind you that this is completely voluntary and you can stop at any time and can still be in the study. Are you ready to begin? Do you have any questions?

NOTE TO RA: Participants will then passively drool into a collection vial for three minutes or until 0.80 milliliters of fluid is collected. Instruct to lean forward, and allow saliva to pool at the bottom of your mouth. Instruct to use tongue to slowly push the saliva into a straw-like collection tool that leads into a tube until you have collected roughly 1 teaspoon of saliva. Immediately put saliva in cooler!

RA: First, I am going to ask you to recall a stressful or traumatic event for a few minutes. Some examples are a serious accident, fire, disaster, physical assault, abuse, war, homicide or suicide. Then, you will write about it and then read or describe it aloud. I can also take notes for you if you prefer to do it that way. You can face whatever direction you want and you can have your eyes open or closed. However, I ask that you try to recall each part of the event in as much detail as you can in your mind's eye. Think of the actions, events, thoughts, feelings, smells, and sensations. Try to remember how you felt and what was happening in your body. Do you have any questions?

I am going to give you a few minutes to imagine the event and write some notes. Here is a pen and some paper. Anything you write will be destroyed after the task.

NOTE TO RA: Give the participant some time to write. Re-iterate any of the instructions if they ask or seem stuck. Stop the procedure if the participant is extremely distressed and contact a Prototypes site staff and [name]. Remind them they can still be in the study if they don't want to complete this part of the procedures.

RA: Now please read what you wrote aloud and vividly imagine it in your mind's eye. (*Time* \sim 5 *minutes*).

NOTE TO RA: 20 minutes after completion, collect saliva samples in an identical manner to the first sample. Participants will then passively drool into a collection vial for three minutes or until 0.80 milliliters of fluid is collected. Instruct to lean forward, and allow saliva to pool at the bottom of your mouth. Instruct to use tongue to slowly push the saliva into a straw-like collection tool that leads into a tube until you have collected roughly 1 teaspoon of saliva. Immediately put saliva in cooler!

POST-TASK DEBRIEFING

Thanks so much for your participation. I know that might have been difficult for you to recall this event. I want to thank you and let you know that we think your participation in this task will help other women who have experienced adversity. While feeling a little distressed might be expected, we want to make sure you are not experiencing a lot of distress. Right now are you are experiencing a lot of distress?

If ves, ask if they want you to get a site staff from Prototypes/Serenity House AND contact the Principal Investigator, [name] [name] *immediately AND* provide [name] contact information to them).

If no, thank them for their time and remind them if anything comes up they can call the Principal Investigator, [name] [name] and/or talk to any of the Prototypes/Serenity House site staff. (Provide [name] contact information to them).

Provide water and snacks at this time and pay close attention to any noticeable changes in mood until they are released to the care of the Prototypes/Serenity House site staff. Immediately inform [name] AND Prototypes/Serenity House site staff of any potential issues.

NOTE TO RA: Please provide the following to the participant (note: can also remind the participant this is also included in the informed consent).

CONTACT INFORMATION

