KEY = Urine collected for drug screen = Saliva collected immediately before & 20 min post trauma imagery task ^a Measures: lifetime trauma exposure (+ occurrence in adulthood, childhood or both); demographics ^b Updated adversity history (traumatic & stressful events, including incarceration), PTSD dx ^c Depression, self-report substance use, perceived stress, mindfulness, fidelity/ adherence to program, quality of life													

Subsection 2.4 - Phase II Recruitment & Screening

The study was designed so that recruitment at Pomona would be paced to match that at the Escondido site so that all procedures across sites happen in tandem, thus avoiding history effects; recruitment data will be evaluated weekly to inform pacing. Site staff at Prototypes will assist with participant recruitment, informing Prototypes residents of the opportunity during formal announcements during programing. Recruitment flyers will also be posted around the RTS. RAs will help recruit women and conduct the initial screening in a private room after obtaining informed consent; progress will be monitored closely by [name] the Lab Management team. Modifications will be made to allow for the study to continue during the COVID-19 pandemic to ensure safety of Ras, site staff, and participants.

Ideally, recruitment will be staggered according to cohorts and paced equally across sites. In total, five cohorts of women will be recruited. Each will have approximately 26- 28 women in each group/site (n=13-14 MBSR; n=13-14 attention control); recruitment proceeds for one month, the intervention runs for approximately 2 months (9 weeks), then there is one month break. *However, this schedule may vary due to COVID-19 restrictions, limitations, and other feasibility issues*.

[name] will explain the study during an initial meeting with potential participants and answer any questions. Then women will be screened for eligibility. Prior to obtaining any data, the women will provide a "consent to screen". This is because we need to obtain data from the women to determine if they are eligible, but they are not officially enrolled as human subjects. By providing their "consent to screen", we are obtaining verbal consent/permission to ask them questions. Their data will not be used by the research team if they are not eligible.

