The following will **not** be eligible for participating:

- 1) Persons who are:
 - a. Not able to speak English
 - Judged to be cognitively impaired, as indicated by score > 10 on the Short-Blessed Screener

Subsection 2.6 - Phase II Laboratory Tests/Sample Collection

Saliva Sampling and Results

Saliva Collection

- Pre-task, saliva will be collected. All saliva collection will occur between 10am-2pm to minimize diurnal fluctuation effects. (Study procedures may start before 10, but first saliva sample must be collected after 10:00am; the second sample must be collected before 2pm participants must be scheduled according to these specifications).
- Two whole saliva samples will be collected using an unstimulated passive drool technique.
- Women will be instructed to avoid eating, brushing teeth, or smoking for one hour prior to the assessment and will be asked to wait to begin the task if they have.
- Participants will rinse their mouths thoroughly with water for 10 minutes before samples are collected. Participants will then passively drool into a collection vial for three minutes or until 0.80 milliliters of fluid is collected.
- Saliva samples will be immediately placed in the on-site freezer (or ice cooler) and be taken to IISBR within 36 hours to be frozen at -80°C until assayed.
- All samples will be assayed for salivary cortisol and CRP using a highly sensitive enzyme immunoassay (Salimetrics, IISBR).
- **Twenty minutes after task completion**, saliva samples will be collected again in an identical manner to that described above.
- Participants will then be offered snacks and a drink and be debriefed to ensure they are not experiencing severe task-related psychological distress. In the unlikely event of participant distress, an immediate referral will be made to on-site professional staff.

Subsection 2.7 - Phase II Intervention Program Description

General Description: Among 134 eligible trauma-exposed homeless women, assess the impact of the MBSR intervention program PTSD symptoms (primary outcomes), and substance abuse, depression, cortisol reactivity, and inflammation (secondary outcomes).

Data Collection Time points: Baseline, 2 months, and 6 months

Total Duration: 6 months

The following sections will outline the intervention process:

- Pre-intervention Assessments
- Brief Stress Task (Trauma Imagery Stress Task)
- Biospecimen Collection
- Biospecimen Analysis
- MBSR Intervention
- Health Promotion Intervention
- Post-Assessment

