- Team Management of Biospecimen Collection Refusal
- Dealing with Program Attrition

Subsection 2.8 - Phase II Pre-intervention Assessments

After Informed Consent, participants will complete a series of self-report measures. These measures will be administered by Research Staff at a private location at the site. Responses options to each question will be provided to the participant, organized in a clearly labeled binder. The Research Staff will display the response options for each measure, read the options out loud, and then record the response on the tablet. At the end of each measure, the RA will "lock" the measure. There will be a prompt if any items have been missed. Please check that there is no missing data. The participant may take a break at any time. However, the participant should refrain from eating, drinking (except for water ~ 10 minutes prior to stress task), or smoking until after the second saliva collection to ensure the accuracy of the saliva sample.

Order of assessments

- 1. Drug test (urine)
- 2. TCU Drug Screen (self-report)
- 3. Self-compassion scale short form
- 4. General self-efficacy scale
- 5. Mindful Attention Awareness Scale
- 6. Difficulties I Emotion Regulation Scale
- 7. Satisfaction with Life Scale
- 8. Quality of Life Enjoyment and Satisfaction Questionnaire
- 9. MOS Social Support
- 10. Perceived Stress Scale
- 11. Dimensions of Anger Reactions
- 12. PROMIS Anxiety
- 13. PROMIS Depression

*NOTE: For time constraints, the urine test can be administered during the waiting period prior to the second cortisol sample.

AT THIS POINT, THE FIRST SALIVARY SAMPLE IS COLLECTED

14. Negative Life Events Inventory

15. PCL 5- *Worst life event* (this is the event that bothers them the most, from their entire life)
16. PCL 5 - *Recent (past year)* this is a traumatic event that has happened to them recently (in the past year) - it may or may not be the same as #16

17. Trauma Imagery Stress Task (the Negative Life Events Inventory and the PCL build up to this)

Subsection 2.9 - Phase II Brief Stress Task (Trauma Imagery Task)

After completing the PROMIS Depression, the participant will provide a saliva sample. They will then complete the negative life events inventory and the PCL 5 (for worst event in their life and a recent event). The reason that the saliva sample is taken before these measures and not directly before the Trauma Imagery Task is because in pilot studies the women began to

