become distressed when recounting their traumas during the Negative Life Events Inventory and the PCL; thus, the "baseline" for cortisol is now taken PRIOR to these items.

After completing the PCL for worst event and recent event, the participant will complete a a modified script-driven imagery task (Seo et al., 2013), derived from prior research with women with PTSD. Participants will be asked to recount a traumatic event via written response. The RA will provide a paper and pen and instruct the participant to recall the event exactly as it happened. The RA can offer prompts to recall sight, smell, and sound. The participant will then recount the event to the RA. Script driven imagery tasks have been effectively and safely used to assess traumatic-stress responses in individuals with PTSD. However, RAs will be highly trained to assess any severe distress that may arise and will immediately notify the PI and site clinical staff immediately. Responses will be subsequently destroyed. *AFTER THE COMPLETION OF THE TRAUMA IMAGERY TASK THE 20 MINUTE POST-SALIVA SAMPLE TIMER STARTS!* When the timer starts, the RA will not interact with the participant. They should sit quietly or may read.

Subsection 2.10 - Phase II Biospecimen Collection

Urine Collection: Participants will provide a urine sample to validate self-report drug use. A 5panel FDA-approved urine test cup will be used in this study. The participant will be instructed to urinate in the cup, close the cup, and then bring it back to the RA to read. Gloves will be used at all times and the RA should read the cup without touching it if possible. The participant will then be instructed to dispose of their urine in the restroom.

Saliva Collection: Before and twenty minutes after the brief stress task (Trauma Imagery Stress Task), women will be asked to provide a salivary sample. Women will be instructed to avoid eating, brushing teeth or smoking for one hour prior to the collection of saliva and will be asked to wait to begin the task if they have. Participants will passively drool into a collection vial for three minutes or until 0.80 milliliters of fluid is collected.

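### The Appendix II script and the Table 4 key place the first saliva sample directly before the imagery task, contrary to Sections 2.8 and 2.9

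*Combined protocol and SAP*

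**What the plan says.** Section 2.8 lists the assessments in order. After item 13 (PROMIS Depression) it states "AT THIS POINT, THE FIRST SALIVARY SAMPLE IS COLLECTED". Items 14 to 16 follow: the Negative Life Events Inventory, then the PCL-5 for the worst event and the PCL-5 for a recent event. The imagery task is item 17.

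Section 2.9 explains this choice. Its explanation opens with "The reason that the saliva sample is taken before these measures and not directly before the Trauma Imagery Task is because in pilot studies", and what the pilot work had found was that participants tended to "become distressed when recounting their traumas during the Negative Life Events Inventory and the PCL". The section's conclusion is that the sample serving as baseline "for cortisol is now taken PRIOR to these items".

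Two other texts give a different point:

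- **Table 4 key (Section 2.3):** "Saliva collected immediately before & 20 min post trauma imagery task".
- **Appendix II script:** after introducing the task, the script instructs "NOTE TO RA: Participants will then passively drool into a collection vial for three minutes or until 0.80 milliliters of fluid is collected". The next line read to the participant is "First, I am going to ask you to recall a stressful or traumatic event for a few minutes".

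Section 2.6 sets the number of samples: "Two whole saliva samples will be collected using an unstimulated passive drool technique". The document contains the protocol twice, and both copies carry the same conflict.

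A smaller conflict sits beside this one. A note in Section 2.8 lets the urine test be done while waiting for the second sample, whereas Section 2.9 bars RA interaction with the participant once the 20-minute timer has started.

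**The concern.** Cortisol reactivity rests on two samples per visit, so the position of the first sample defines the measure. The protocol recognised that its trauma questionnaires are themselves stressful and moved the baseline ahead of them. The script the RA reads at the moment of collection, and the table summarising the schedule, do not reflect that move.

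A baseline taken at the script's point could already contain part of the stress response. If some staff followed the script and others Section 2.8, the measure would also differ in kind between women and between visits. Arms are assigned by site and cohort, and the SAP model has no term for sampling order, so uneven practice would go unadjusted.

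**Working it through.** The plan states no figure to reproduce. The check compares the texts, then counts what lies between the two sampling points.

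**1. The texts side by side**

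| Source | Position of first sample | Relation to items 14–16 |
|---|---|---|
| Section 2.8 | After item 13 | Before |
| Section 2.9 | Ahead of the inventory and PCL-5s; expressly not directly before the task | Before |
| Table 4 key | Immediately before the task (item 17) | After |
| Appendix II script | After the task introduction, with recall next | After |
| Sections 2.6 and 2.10 | Pre-task, or before the task | Fits either order |

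**2. Could the script's collection be an additional sample?** Following Section 2.8 and the script literally gives 1 (Section 2.8) + 1 (script, pre-task) + 1 (post-task) = 3 collections, against 2 in Section 2.6. The script's later note also refers back to its earlier collection as the first sample. The texts therefore describe one sample at two different points.

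**3. Could items 14–16 fit inside the script?** The script has no break between the collection and recall, and its spoken overview runs sample, task, sample.

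**4. Items between the two points**

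- Life-events inventory: 40 events (Appendix IV).
- PCL-5: 20 symptom items (Appendix IV), given twice at baseline (Section 2.8).
- Baseline total: 40 + 20 + 20 = 80.
- Follow-up: not established. Section 2.4 names only the recent event, and the two-PCL order in Section 2.8 is headed pre-intervention. The load is 20 or 40 PCL-5 items plus the life-event update.

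**5. Time, for scale only.** The documents give no duration for these items. Assume 5 to 30 seconds per item:

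- 80 × 5 s = 400 s, about 7 minutes.
- 80 × 30 s = 2,400 s = 40 minutes.
- The definitions section says cortisol is released about 20 minutes after a stressor. 20 minutes = 1,200 s, and 1,200 / 80 = 15 s per item, which lies inside the assumed range.

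**6. Direction.** Take reactivity as post-task minus pre-task cortisol (an assumption, since no formula is given). Let b be the undisturbed baseline, p the post-task level, and r the part of the response already present at the script's sampling point. The measured value is p − (b + r) = (p − b) − r, so any r > 0 understates reactivity. The documents contain no data from which to estimate r.

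**7. The urine note.** Section 2.10 has the participant bring the cup to the RA to be read. Done during the wait, that is an interaction of the kind Section 2.9 excludes. Section 5.3 lets the woman choose to take the test before or after the interview, which does not remove the conflict.

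**The case against.** The best reply is that the protocol settles the matter itself. Section 2.8 marks the point in capitals and Section 2.9 explains it, so what remains is leftover wording. That is right about the intention, but the script is the text in use at the moment of collection and it gives a different instruction.

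A milder reading is also possible: if the script's opening were read out at the Section 2.8 point, items 14–16 would come before recall and the order would be correct. The script does not say this, and the reading does not rescue the Table 4 key, which states the timing that Section 2.9 rejects.

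The time range has no evidential base, and the 15-second figure treats a rough lag as a threshold that starts at the first item. That stands; the figures are illustrative only. The count of 80 also omits the age questions for each life event and the PCL-5 exposure questions, so it is not a full measure of the load.

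The SAP is written in the past tense, which suggests that collection may be over, and editing the script would then change no data. That stands too, and leaves mainly a reporting step. Finally, the urine note is a separate, minor matter; it is included because it affects the same pair of samples.

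**Conclusion.** The concern holds. The script and the table key contradict Sections 2.8 and 2.9 on when the cortisol baseline is drawn, and the instructions cannot all be followed with two samples. That the script and key were simply not updated is an inference, supported by the wording of Section 2.9.

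The matter should be corrected but is limited in reach. It concerns cortisol reactivity, one of several secondary outcomes. If the script was followed, the likely direction is understatement, on the assumption that the inventory and PCL-5s raise cortisol as Section 2.9 implies. The size cannot be estimated from the documents. Nothing shows that a sample was actually mistimed, and staff training may have prevented it.

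**What to change.** **In the protocol**

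- Move the first collection instruction in Appendix II to the point marked in Section 2.8, and reword the script's overview sentence to match.
- Change the Table 4 key to say that the first sample precedes the Negative Life Events Inventory.
- Reconcile the Section 2.8 urine note with the no-interaction rule in Section 2.9.
- Make sure that both sample times and the order used are recorded at each visit.

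**For data already collected**

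- Report which order was used.
- If the order was recorded and varied, add a sensitivity analysis of cortisol reactivity restricted to samples taken in the Section 2.8 order.
- If the order is unknown, state that as a limitation.

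**Cost.** Edits to the script, the key and one note, plus a short message to RAs. Whether REDCap needs new fields cannot be judged, because the Appendix VII forms are not in the text provided. If collection is complete, the cost is one statement of the order used, and one sensitivity analysis only where the records allow it.

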Arm: The different groups of the intervention. In this study, Arm 1 is the health promotion attention control and Arm 2 is the MBSR. Participants at a given site are assigned to one Arm or the other, by cohort).

Cohort: The group of people that are doing the interventions at the same time.

Cortisol: The body's main stress hormone, triggered by the adrenal glands. Cortisol is a glucocorticoid and is released in the body about 20 minutes after a stressor. The immediate stress response hormones (adrenaline and epinephrine) are released within seconds or minutes; if the brain continues to perceive something as stressful, then cortisol is released.

C-Reactive Protein (CRP): This is a protein made in the liver. CRP tends to increase when there is inflammation occurring in the body, (Lindqvist et al., 2014, 2017) induced by proinflammatory cytokines in the liver (Eklund, 2009). These heightened inflammatory responses can lead to health impairments including atherosclerosis (Wong et al., 2012) and cardiovascular disease (Coughlin, 2011) compounding health disparities in disadvantaged populations; CRP, in particular, has been linked with obesity (Visser et al., 2011) metabolic syndrome (Ridker et al., 2003) and CVD.(Ridker et al., 1998) Thus CRP can be used as marker for general inflammation and risk for inflammatory-related problems.

Other acronyms used in this protocol:

IISBR - Institute for Interdisciplinary Salivary Bioscience Research - https://iisbr.uci.edu/

- IISBR is a shared resource and scientific hub; researchers can gain practical experience/knowledge in salivary bioscience through the training programs (e.g., Spit

Camp). IISBR also provides the storage and analyses of the salivary samples collected in this study.

SECTION 1B. INTRODUCTION TO PTSD AND MBSR

Subsection 1B.1 - PTSD Basics

PTSD Diagnosis

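### Appendix II gives staff two saliva end points about six-fold apart in volume, so the timing of the post-task cortisol sample is not fixed

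*Combined protocol and SAP*

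**What the plan says.** The saliva collection rule appears in three places in the protocol.

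- **Section 2.6 (Saliva Collection):** "Participants will then passively drool into a collection vial for three minutes or until 0.80 milliliters of fluid is collected". The second sample comes "Twenty minutes after task completion" and is taken in the same way.
- **Section 2.10 (Biospecimen Collection):** "Participants will passively drool into a collection vial for three minutes or until 0.80 milliliters of fluid is collected".
- **Appendix II (Trauma Imagery Script):** the staff note for the first sample repeats the rule, "passively drool into a collection vial for three minutes or until 0.80 milliliters of fluid is collected". It then coaches posture and tongue movement and ends that instruction with "until you have collected roughly 1 teaspoon of saliva". The note for the second sample opens with "20 minutes after completion, collect saliva samples in an identical manner to the first sample" and repeats both end points.

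The combined file contains the protocol twice, so the two notes appear in four places. Neither Section 2.6 nor Section 2.10 mentions a teaspoon. No section states a saliva flow rate or how long a teaspoon should take to collect.

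On the purpose of the timing, the Basic Definitions section says: "Cortisol is a glucocorticoid and is released in the body about 20 minutes after a stressor". Section 2.9 starts a 20-minute timer when the imagery task ends.

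**The concern.** A teaspoon is several times 0.80 mL, so anyone who collects one has already passed the volume limit stated two sentences earlier. The two instructions cannot both be followed, and the script does not say which governs. The conflict sits in the working script that research assistants follow at the visit, for both samples and at all three assessments.

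Cortisol reactivity is a named secondary outcome and rests on only two samples per visit. The plan takes visible care over their timing: a fixed timer, a 10am to 2pm window, and a first sample moved ahead of the trauma questionnaires to protect the baseline. If some staff stop at 3 minutes or 0.80 mL and others collect until the tube holds a teaspoon, the post-task sample no longer covers a standard interval. The departure would be largest in women with low saliva flow.

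**Working it through.** **Inputs from the documents.** Volume limit 0.80 mL; time limit 3 minutes; post-task collection starts 20 minutes after the task ends (Sections 2.6 and 2.10, Appendix II).

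**Inputs not in the documents.** One teaspoon is 4.93 mL (US) or 5 mL (metric) by unit definition. Flow rate is assumed and varied below. The plan gives no duration for a teaspoon, so there is no stated figure to reproduce.

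**Volume ratio.** 4.929 / 0.80 = 6.16 (US); 5.0 / 0.80 = 6.25 (metric). This step does not depend on flow.

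**Flow needed to satisfy the teaspoon and the 3-minute limit together.** 4.929 / 3 = 1.64 mL/min.

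**Timing of the post-task sample for an assumed flow f (US teaspoon).**

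- Teaspoon line: duration = 4.929 / f; end = 20 + duration; midpoint = 20 + duration / 2.
- 3 minutes or 0.80 mL, read as the first limit reached: end = 20 + the smaller of 3 and 0.80 / f.

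| Assumed flow (mL/min) | Teaspoon duration (min) | Teaspoon end (min) | Teaspoon midpoint (min) | End under 3 min / 0.80 mL (min) |
|---|---|---|---|---|
| 0.1 | 49.3 | 69.3 | 44.6 | 23.0 |
| 0.2 | 24.6 | 44.6 | 32.3 | 23.0 |
| 0.267 (= 0.80 / 3) | 18.5 | 38.5 | 29.2 | 23.0 |
| 0.3 | 16.4 | 36.4 | 28.2 | 22.7 |
| 0.5 | 9.9 | 29.9 | 24.9 | 21.6 |
| 1.0 | 4.9 | 24.9 | 22.5 | 20.8 |

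With a metric teaspoon the end times at 0.1, 0.267 and 1.0 mL/min are 70.0, 38.75 and 25.0 minutes.

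**Spread between women over the assumed flows.** Under the teaspoon line the end time ranges over 69.3 − 24.9 = 44.4 minutes. Under the 3-minute or 0.80 mL rule it ranges over 23.0 − 20.8 = 2.2 minutes.

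**Status of the 0.267 mL/min row.** Three minutes and 0.80 mL are alternative limits. A woman who reaches 0.80 mL before 3 minutes has a faster flow than this, and one stopped by the clock has a slower one. The row is one scenario in the range, not a rate that the protocol gives.

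**The case against.** The strongest reply is that the teaspoon line is loose coaching on technique, addressed to the participant and placed after a clear numeric limit. Sections 2.6 and 2.10 repeat that limit, and Section 2.20 provides competency checks and mock sessions. Staff may well have stopped at 3 minutes whatever the later sentence says. This stands as a reason not to assume a delay occurred. It does not remove the conflict: the line is worded as an end point and is the last one before the tube goes into the cooler.

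A reader might infer several stronger things that the documents do not support.

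- **That the 20-minute sample becomes a 38-minute sample at the protocol's own flow rate.** No flow rate is stated. Collection would still start at minute 20; minute 38.5 is when it would end in one assumed scenario, with a midpoint near 29.
- **That the sample would average over cortisol recovery.** The protocol gives only the approximate 20-minute release time and no recovery course. Section 2.9 also notes that women became distressed during the questionnaires before the task, so time since stress onset already varies.
- **That the 2pm cut-off is threatened.** In the 0.267 mL/min scenario two teaspoon collections take 2 × 18.5 = 37 minutes against 2 × 3 = 6, an extra 31 minutes in a four-hour window. Nothing shows that this is binding.
- **That the arms are biased relative to each other.** One script serves both arms. Each site runs one arm per cohort, so differing staff habits could line up with arm within a cohort, and the SAP describes a site effect but no cohort term. That is a possibility only; no document shows that practice differed.

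**Conclusion.** The contradiction is real and does not depend on any assumption about flow: one note gives two end points that differ about six-fold in volume, and the script departs from Sections 2.6 and 2.10. The effect on timing is conditional. It arises only if staff followed the teaspoon line over the 3-minute limit, and its size depends on flow. For assumed flows of 1.0 to 0.1 mL/min, post-task collection would end at about minute 25 to 69, against minute 23 at the latest under the other rule. The minute-23 bound takes the first limit reached as the stopping point, which is the natural reading but is not spelled out; at 0.1 mL/min, 0.80 mL alone would take 8 minutes.

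The consequence is poorer standardisation of one secondary outcome, cortisol reactivity, between women, staff and visits. The documents give no basis for estimating the effect on cortisol values, their variance or the group comparison. The PCL-5, the sample size and the error rate are untouched.

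**What to change.** Reconcile the script with Sections 2.6 and 2.10: remove the teaspoon end point from the pre-task and post-task notes in Appendix II, in both copies of the protocol (four places). If the first limit reached is meant to govern, say so in the same line. Have staff record the start and stop time of each collection. The cost is a one-line correction, a reminder to staff and two time fields per sample.

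The SAP reports its analyses in the past tense, and the recruitment timeline ends in early 2023, so collection may be over. In that case the sponsor should state which end point staff used and check any recorded volumes or times, by site and cohort where possible, before interpreting cortisol reactivity. If neither was recorded, that should be reported as a limitation of this outcome.
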